9.7.3 Visit 1 characteristics

Visit 1 demographic information including body measurements will be summarised and listed. In addition, all Visit 1 details on adverse drug reactions, and adverse drug reactions of special interest (anti-FXIII antibodies, allergic reactions, embolic and thrombotic events and lack of therapeutic effect), result of blood sample for FXIII activity and anti-FXIII antibodies, diagnosis of FXIII deficiency, history of bleeding episodes, bleeding treatment, medical history, vital signs, predefined complication, concomitant medication and illness and history of FXIII antibodies will be summarised and listed.

9.7.4 Other assessments

9.7.4.1 Product dose

Assessment of doses of rFXIII will be summarized and listed.

9.7.4.2 FXIII activity

Assessments of FXIII activity will be summarised and listed.

9.7.4.3 Vital signs

Vital Signs will be summarised and listed.

9.7.4.4 Surgery events

Frequency of all surgery events will be summarised by magnitude (minor or major), indication and name of surgery.

Surgery events will be listed including also information of time period, total number of injections and dose as well as haemostatic response during and after surgery.

Haemostatic response during surgery and after surgery will further be summarised.

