- Site of bleeding (central nervous system bleeding (divided into intracranial haemorrhage or other), haemarthrosis, gastrointestinal bleeding, subcutaneous bleeding, muscular bleeding or other).
- Date and time of bleeding arrest.

Definition of severity of bleeds

- Mild/Moderate: Minor uncomplicated bleeds.
- **Severe:** Major bleeds which require hospitalisation. All head, central nervous system and neck bleeds must be categorised as severe.

All mild or moderate bleeds which are active after 24 hours will change category to severe and the treatment responsibility should preferably be transferred to the Physician.

Definition of haemostatic response

- **Excellent:** abrupt pain relief and/or substantial improvement in signs of bleeding within approximately 8 hours after a single infusion.
- Good/Effective: some pain relief and/or improvement in signs of bleeding within approximately 8 hours after infusion of product, but not requiring more than one infusion for complete bleeding arrest.
- Moderate/Partly effective: slight beneficial effect on pain relief and/or minimal improvement in signs of bleeding within approximately 8 hours after the first product infusion, but not requiring more than one infusion for complete bleeding arrest.
- None: no improvement or worsening of symptoms or use of other FXIII products.

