9.3.4.2 Surgery events

For all surgery events the following will be recorded, if available:

- Surgery description and indication (elective or emergency).
- Surgery type (minor or major surgery).
- Duration surgery hours (start and stop time of surgery).
- Haemostatic drug used in connection with surgery, beyond the monthly prophylactic rFXIII dose (covering other products and rFXIII, if used):
 - Drug name/product name.
 - Date and time of treatment

Protocol Date: 02 February 2016 Novo Nordisk Study ID: NN1841-3868 Version: 2.0

Final

40 of 65

 Study ID: NN1841-3868
 CONFIDENTIAL
 Version:

 UTN: U1111-1131-1558
 Status:

 EU PAS No.: ENCEPP/SDPP/3687
 Page:

• Dose and regimen.

- Haemostatic response during surgery (see section 9.3.4.2).
- Haemostatic response after surgery (see section 9.3.4.3).
- Blood products transfusion (yes/no):
 - Type (red blood cells, FFP platelets, or other).
- Adverse drug reactions, serious adverse events and medical events of special interest in connection with administration of the product.
- Allergic reactions (please refer to section 9.3.3.1).
- Embolic and thrombotic events (please refer to section 9.3.3.1).
- Lack of therapeutic effect (please refer to section 9.3.3.2), assessed as haemostatic response.

Definition of major surgery

Major surgery is any invasive operative procedure where any one or more of the following occur:

- A body cavity is entered.
- A mesenchymal barrier (e.g., pleura, peritoneum or dura) is crossed.
- A fascial plane is opened.
- An organ is removed.
- Normal anatomy is operatively altered.

These procedures may be performed using general anaesthesia, spinal anaesthesia, epidural anaesthesia, conscious sedation or with a combination of these modalities.

Definition of minor surgery

Minor surgery is any invasive operative procedure in which only skin, mucous membranes, or superficial connective tissue is manipulated. Examples of minor surgery include vascular cut down for catheter placement, implanting pumps or ports in subcutaneous tissue, biopsies or placement of probes, leads, or catheters requiring the entry into a body cavity only through a needle/guidewire.

Dental surgery will be classified as minor or major based on above definitions.

Haemostatic response during surgery

Clinical evaluation of haemostatic response during surgery will be evaluated as follows:

- **Excellent:** blood loss less than expected.
- Good: blood loss as expected.

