Use of rFXIII in patients with congenital FXIII A subunit deficiency, other than for prophylactic treatment will listed with patient ID, site, age and alternative purpose of the administration of rFXIII. A subsection for product doses should be added.

Annualised Bleeding rate

This secondary endpoint comprises the annualised rate of bleeding (covering both treatment requiring and non-treatment requiring), occurring from first study related activity after signing the informed consent to the end of patient's participation in the study.

Annualised bleeding rate will be summarised by cause (spontaneous, traumatic and surgery), therapeutic regimen (prophylactic therapy, on-demand therapy, surgery) severity, site of bleeding, haemostatic treatment administered (product name) and haemostatic response. The ratio between traumatic and spontaneous bleeding rates will further be summarised and listed and graphical displays of the bleeding rates and the referred ratio will be presented by patient, ordering the patients according to increasing values.

Protocol	Date:	02 February 2016	Novo Nordisk
Ct., dr. ID. NN11041 2060	Varaion:	2.0	

 Study ID: NN1841-3868
 CONFIDENTIAL
 Version:
 2.0

 UTN: U1111-1131-1558
 Status:
 Final

 EU PAS No.: ENCEPP/SDPP/3687
 Page:
 47 of 65

Bleeding episodes will further be listed, including information about cause, severity, location, date and time of onset, date and time of arrest, product name, dose, haemostatic response, related concomitant illness and related concomitant medication.

Presentation by previously untreated patients

To the extent that the study enrols patients, who receive their first administration of rFXIII within the scope of the present study, a separate presentation of both primary and secondary endpoints will be conducted for this group of patients.

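### The bleed response scale rates any use of another FXIII product as None, mixing treatment with outcome; the surgery response outputs also leave the product unnamed

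*Protocol*

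**What the plan says.** **Bleeds.** Section 9.3.4.1 collects, for each bleed treated with a FXIII-containing product or an antifibrinolytic, the drug, its timing, its dose and the treatment outcome on a four-level scale. *Excellent* and *Good/Effective* are defined by pain relief or improvement in bleeding signs within about 8 hours and by the number of infusions. Neither refers to a particular product. *None* is defined as "no improvement or worsening of symptoms or use of other FXIII products".

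Section 9.7.2.2 names, among the dimensions by which bleeding is summarised, "haemostatic treatment administered (product name) and haemostatic response". It also lists product name, dose and response for each episode.

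**Surgery.** Section 9.3.4.2 records the name of any haemostatic drug given beyond the monthly prophylactic dose, whether rFXIII or another product. In section 9.7.4.4, "Frequency of all surgery events will be summarised by magnitude (minor or major), indication and name of surgery". Events are to be "listed including also information of time period, total number of injections and dose as well as haemostatic response during and after surgery", and then "Haemostatic response during surgery and after surgery will further be summarised". Product is named in none of these three outputs.

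**The concern.** A response scale should grade what happened to the bleed. Here one route into the worst grade is a fact about treatment. A bleed managed with another FXIII product can therefore be graded as a failure when it stopped promptly.

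The rating is made when the data are collected, by the patient in the diary and by the physician in the CRF. If raters follow the words, the observed response is overwritten. If some follow the words and others the apparent intention, the same clinical course gets different grades. An analysis plan written later cannot reliably undo either.

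Such bleeds are foreseeable. Under section 9.2.4, interrupting or stopping rFXIII is not a reason to leave the study, and section 9.3 asks for other haemostatic products to be recorded. One secondary objective is to assess rFXIII used other than for prophylaxis. The response data for bleeds and surgery are where a reader would look to see how it performed, so they need to be readable by product.

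**Working it through.** The documents give no figure to reproduce. The check sets definitions beside collection and reporting.

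1. **Which bleeds are rated.** All bleeds treated with any FXIII-containing product or an antifibrinolytic (9.3.4.1). The scale is therefore applied to products other than rFXIII.
2. **What puts a bleed in *None*.** Three alternatives joined by 'or': no improvement, worsening, or use of other FXIII products. Any one suffices. Nothing restricts the third to a switch made after a first product failed.
3. **Whether the grades exclude one another.** Take a bleed treated only with another FXIII product that improves substantially within about 8 hours of one infusion. It meets *Excellent* on outcome and *None* on product. The scale gives no rule for choosing.
4. **Comparison within the protocol.** The post-operative scale in 9.3.4.3 ties its *None* grade to inadequate therapeutic effect that requires a change of regimen. The bleed scale has no such link between the other product and an inadequate effect.
5. **Where the grade goes.** Product and response are both summary dimensions in 9.7.2.2 and appear side by side in the episode listing, so the conflicting grade reaches the report.
6. **Surgery.** Product is collected in 9.3.4.2. Section 9.7.4.4 names strata for the frequency of surgery and some contents of the listing. Product is in neither, and the response summary has no stated breakdown. Section 9.7.2.2 does name product for bleeds.

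**Illustration only; every number is assumed.** Let 10 treated bleeds all stop well, with *m* of them treated solely with another FXIII product. On the literal rule, the proportion graded better than *None* is (10 − *m*)/10:

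- *m* = 1: 9/10 = 90%
- *m* = 2: 8/10 = 80%
- *m* = 5: 5/10 = 50%

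The clinical result is 10/10 = 100% in each case. The documents give no value for *m*.

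**The case against.** The best defence is that the clause was meant for rescue. Treatment outcome is recorded within the entry for the drug used, so 'other' can mean other than the product being rated. The neighbouring grades are anchored on what follows an infusion, which fits a reading of 'a different product was needed'. On that reading, a bleed treated first with a plasma-derived product is graded on its own course. This is plausible and probably the intention, but it is not written, and raters work from what is written.

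On surgery, the defence is stronger. The listing contents are introduced in a way that is not exhaustive, table strata are commonly left to the analysis plan, and the section sits under other assessments rather than the endpoints. Splitting surgeries by cover in a study expecting a minimum of 30 patients will also give sparse cells. All of this stands, which is why the surgery change is only a companion.

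A reader might infer four stronger things that the documents do not support:

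- *Response is not linked to product for bleeds.* It is: product and outcome are recorded together and listed together.
- *A product-by-response table for bleeds is planned, with a fixed failure row.* Section 9.7.2.2 names the two dimensions but states no cross-tabulation.
- *Surgical responses will be pooled over products.* The protocol is silent on this; it does not say so.
- *A poor surgical response under another product enters the primary endpoint.* Surgical lack of effect is indeed "assessed as haemostatic response" with no product condition. But the primary endpoint counts adverse drug reactions, and section 11.2.2 requires a suspected causal relationship with the product. Such a case could be reported as a medical event of special interest, which section 11.2.4 collects regardless of causality; there it is listed with its relationship to study drug.

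**Conclusion.** The point holds for the bleed scale. As written, *None* mixes treatment with outcome and overlaps with *Excellent* and *Good/Effective*. Response data for bleeds treated from the outset with another FXIII product will be wrong if the words are followed and inconsistent if they are not.

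Its size cannot be stated. On the literal reading all such bleeds are affected, but the documents do not indicate how many there will be. The account of existing treatment options in section 7.2 is general background and does not show that they will be common among enrolled patients, who have actual or planned rFXIII exposure. The conclusion assumes only that at least some bleeds are treated first with another FXIII product, which the protocol allows. Bleeds treated only with rFXIII are untouched.

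For surgery, the finding is limited to a missing label: the response summary and listing do not name a product that is already collected.

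**What to change.** **Section 9.3.4.1.** Restrict the third clause of *None* to use of a different FXIII product because the response to the product being rated was insufficient. State that a bleed treated first with another product is rated on that product's effect and shown under that product. Carry the same wording into the diary and CRF instructions, since the grade is assigned there.

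**Section 9.7.4.4 (minor).** Add product name to the surgery listing. Show response during and after surgery separately for surgeries with additional rFXIII, with prophylactic rFXIII only, and with another product.

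The cost is a line of wording, one listing column and one table split. No new data are needed, because product is already on the CRF. The drawback is small cells in the surgery table; where they are too sparse to summarise, the listing carries the information. The changes concern measurement and reporting only, not treatment.

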9.7.4.5 Concomitant illness and medication

Concomitant illness and medication will be summarised and listed.

 Study ID: NN1841-3868
 CONFIDENTIAL
 Version:
 2.0

 UTN: U1111-1131-1558
 Status:
 Final

 EU PAS No.: ENCEPP/SDPP/3687
 Page:
 48 of 65

9.7.4.6 Home treatment

Treatment administration recorded according to the patient diary will be summarised and listed.

9.7.4.7 Pregnancies

Pregnancies will be summarised and listed.

9.7.5 Interim analysis

An interim report is to be performed every two years after study start (FPFV). The interim report will include all the statistical descriptions listed in section 9.7.2.

9.7.6 Sequential safety analysis/safety monitoring

An annual status report will be developed for reporting to relevant Health Authorities; this is to be in connection with the Periodic Safety Update Report (PSUR) reporting to European Medicines Agency (EMA).

9.8 Quality control

9.8.1 Monitoring procedures

During the course of the study, the monitor should visit the study site at intervals. The purpose of these visits is to ensure that the CRFs are completed correctly, the protocol is adhered to, and to collect completed CRF pages. Data for at least 20% of the enrolled patients will be source data verified. The monitor will ensure that the CRFs are collected.

9.8.2 Critical documents

Before the Physician starts the study (i.e., obtains informed consent from the first patient), the following documents must be available at Novo Nordisk:

- Regulatory approval and/or notification as required
- Curriculum Vitae (CV) of Physician (current, dated and signed and/or supported by an official regulatory document)
- Signed and dated agreement on the final protocol
- Signed and dated agreement on any amendment(s), if applicable
- Approval/favourable opinion from IEC/IRB clearly identifying the documents reviewed: the protocol, any amendments, patient information/informed consent form and any other written information to be provided to the patient, patient enrollment procedures
- Copy of IEC/IRB approved patient information/informed consent form/any other written information/advertisement
- Non-interventional study agreement

Study ID: NN1841-3868 UTN: U1111-1131-1558 EU PAS No.: ENCEPP/SDPP/3687 Version: 2.0
Status: Final
Page: 49 of 65

9.8.3 Retention of study documentation

Patient notes must be kept for the maximum period permitted by the hospital, institution or private practice.

Novo Nordisk will comply with all the requirements of Good Pharmacoepidemiological Practice (GPP) and relevant national legislation related to archiving of study documentation. Records containing patient sensitive data must not be archived by Novo Nordisk, but must be kept with Physician and patient and according to local regulations pertaining to personal data protection.

The Physician must agree to archive the documentation pertaining to the study in an archive after completion or discontinuation of the study, if not otherwise notified. The Physician should not destroy any documents without prior permission from Novo Nordisk.

Novo Nordisk will retain the documentation pertaining to the study according to company procedure and in accordance with national regulations if they require a longer retention period.

9.8.4 Archiving of statistical programs

The final programs and outputs, and all relevant documentations used in the process of reporting the study will be archived.

9.9 Limitations of the research methods

As this is a non-interventional PASS there will be a number of potential confounding factors, which are controlled in randomised clinical trials. This involves selection bias of patients in relation to the willingness or ability to cooperate in a study like the non-interventional PASS with a diary. In addition the use of a patient diary introduces an increased risk of incorrectness of dose and bleeding evaluation; this will be minimised by review of the diary by the Physician before entering into the CRF. Concerning the issues of bleeding evaluation of home treatment the risk of misclassification is especially relevant. To minimise misclassification the patient and the Physician will evaluate the bleeding episodes together at the next visit, see section 9.3.5.1. Inconsistency checks and further medical checks by qualified medical persons to capture and resolve inconsistencies will be performed.

9.10 Other aspects

Not applicable section, as all aspects of the research method are covered by the previous sections.

02 February 2016 | Novo Nordisk Protocol Date:

EU PAS No.: ENCEPP/SDPP/3687

Study ID: NN1841-3868 Version: 2.0 UTN: U1111-1131-1558 Status: Final Page: 50 of 65

Protection of human subjects

The study will be conducted in accordance with Good Pharmacoepidemiology Practice (GPP¹¹), applicable regulatory requirements, and in accordance with the Declaration of Helsinki 12,13.

The burden added to the patient's life by participating in this study: is entering data into a diary. The diary for home treatment is recommended or required by most centers and will thus serve a disease management purpose apart from the purpose of reporting to the study. The potential benefits for the patient are the systematic assessments of safety, especially comprising anti-FXIII antibodies and lack of effect.

There are no risks associated with this activity. It is thus evaluated that the benefits outweigh the extra burden and risks associated with participating in this study.

When a patient's participation in the study ends, the patient will consult with the physician to decide on the best available treatment

10.1 Informed consent form for study patients

Informed consent from all study participants is required before any data is entered into the CRF and/or any blood samples are sent to the Central Laboratory for analysis.

In obtaining and documenting informed consent, the physician must comply with the applicable regulatory requirement(s) and adhere to the requirements in the Declaration of Helsinki $\frac{12,13}{2}$.

Prior to any study-related activity, the physician must give the patient and/or the LAR oral and written information about the study in a form that the patient or the patient's LAR can read and understand. This includes the use of impartial witness where required.

A voluntary, signed and personally dated, informed consent form will be obtained from the patient and/or the patient's LAR prior to any study-related activity.

If the patient is under age, the physician and the parents/patient's legally acceptable representative will evaluate if the patient is at a level of maturity whereby the patient can sign the informed consent. National regulation on obtaining informed consent from patients under age must be observed. This signature does not substitute the signature of the parent(s) or the patient's LAR.

The task of seeking informed consent can only be performed by the physician or another medically qualified person delegated by the physician, if permitted by local regulation, who must sign and date the patient information/informed consent form.

Protocol		Date:	02 February 2016	Novo Nordisk
Study ID: NN1841-3868	CONFIDENTIAL	Version:	2.0	

UTN: U1111-1131-1558 CONFIDENTIAL Status: Final EU PAS No.: ENCEPP/SDPP/3687 Page: 51 of 65

If information becomes available that may be relevant to the patient's willingness to continue participating in the study, the physician must inform the patient and/or the patient's LAR in a timely manner and a revised written informed consent must be obtained.

10.2 Data handling

If the patient (or the patient's LAR) withdraws the previously given informed consent the patient's data will be handled as follows:

- Data collected will be used as part of the study population.
- Safety events will be reported to the department responsible for Global Safety, Novo Nordisk/regulatory authorities.

If data is used, it will always be in accordance with local law and IRB/IEC procedures.

10.3 Institutional Review Boards/Independent Ethics Committee

Before commencement of the study, the protocol, any amendments, patient information/informed consent form, any other written information to be provided to the patient, patient enrolment procedures, if any, package insert, the physician's current CV and/or other documentation evidencing qualifications, and other documents as required by the local institutional review board (IRB)/independent ethics committee (IEC) should be submitted. The submission letter should clearly identify (by study identification number, including version, title and/or date of the document) which documents have been submitted to the IRB/IEC. Written approval/favourable opinion must be obtained from IRB/IEC or another relevant scientific body according to local legislation before commencement of the study.

During the study, the physician must promptly in accordance with local requirements report the following to the IRB/IEC: unexpected serious adverse drug reactions where a causal relationship cannot be ruled out, amendments to the protocol according to local requirements, deviations to the protocol implemented to eliminate immediate hazards to the patients, new information that may affect adversely the safety of the patients or the conduct of the study (including new risk/benefit analysis in case it will have an impact on the planned follow-up of the patients), annually written summaries of the study status and other documents as required by the local IRB/IEC.

Amendments must not be implemented before approval/favourable opinion, unless necessary to eliminate immediate hazards to the patients.

The physician must maintain an accurate and complete record of all submissions made to the IRB/IEC. The records should be filed in the physician's study file and copies must be sent to Novo Nordisk.

02 February 2016 | Novo Nordisk Protocol Date: Version: 2.0

Study ID: NN1841-3868 UTN: U1111-1131-1558

Status: Final EU PAS No.: ENCEPP/SDPP/3687 Page: 52 of 65

